1.3 Secondary Objectives

- To evaluate clinical efficacy of immunotherapy in combination with rituximab in relapsed/refractory or untreated FL as measured by:
 - Objective response rate (2014 Lugano¹)
 - Overall and complete response rate (LyRIC²)
 - PFS, overall survival (OS), and time to next treatment (TTNT)
 - PFS will be analyzed by both 2014 Lugano¹ and LyRIC² criteria
 - Objective response rate, complete response rate, and MRD negativity will be stratified by grade (1-2 versus 3A) and by FL International Prognostic Index (FLIPI)³
- Evaluate safety of these combinations in relapsed/refractory FL and previously untreated FL.
 - Rate of grade 3 or higher toxicity regardless of attribution
 - Rate of grade 3 or higher toxicity at least possibly related to study treatment

• Rate of grade 2 or higher toxicity at least probably related to study treatment

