Toxicity will be continuously monitored and recorded using CTCAE 4 criteria, up to 30 days following the last dose of the study treatment or until resolution of toxicity to grade 1 or baseline, whichever occurs last. Response will be assessed 4-6 weeks after the completion of therapy (either after cycle 6 of therapy for patients who complete the planned cycles of therapy, or after their last dose of treatment for patients who discontinue treatment before cycle 6) by PET and CT scans of the neck (if involved at baseline), chest, abdomen, and pelvis, as well as at 6, 12, and 18 months from the end of treatment (+/- 2 weeks) in the absence of disease recurrence or progression (PET may be omitted once patient is in CR). In addition, CT scans of the chest, abdomen, and pelvis +/- neck will be obtained 4 weeks (+/- 1 week) after the completion of cycle 3 while on therapy. If patients experience evidence of progressive disease confirmed by imaging while on treatment, they will be allowed to complete treatment if they meet the definition of an indeterminate response according to LyRIC criteria.²

Expected toxicities and potential risks for all drugs are described in Section 6 (Dosing Delays/Dose Modifications). No investigational or commercial agents or therapies other than those described below may be administered with the intent to treat the participant's malignancy.

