7.2 Adverse Event Reporting

In the event of an unanticipated problem or life-threatening complications treating investigators must immediately notify the Overall PI.

Investigators **must** report to the Overall PI any adverse event (AE) that occurs after the initial dose of study treatment, during treatment, or within 30 days of the last dose of treatment on the local institutional SAE form.

The study period, during which AEs and SAEs must be reported, begins after starting the first dose of study treatment and ends 30 days following the last administration of study treatment or study discontinuation/termination, whichever is earlier. After this period, investigators should only report SAEs that are attributed to study treatment. All AEs and SAEs whether volunteered by the subject, discovered by study personnel during questioning, or detected through physical examination, laboratory test, or other means will be assessed and reported, when appropriate. Abnormal laboratory values will not be reported unless deemed to be clinically significant. Each reported AE or SAE will be described by its duration (i.e., start and end dates), regulatory seriousness criteria if applicable, suspected relationship to study therapy, expectedness, and actions taken.

The table below summarizes the requirements for recording safety events on the CRF and for reporting safety events. These requirements are delineated for 3 types of events: (1) SAEs;

(2) non-serious adverse events (AEs); and (3) exposure to the investigational product under study during pregnancy or breastfeeding, and occupational exposure.

For Multi-Center Trials where a DF/HCC investigator is serving as the Sponsor, each participating institution **must** abide by the reporting requirements set by the DF/HCC. This applies to any medical event equivalent to an unexpected grade 2 or 3 with a possible, probable or definite attribution, unexpected grade 4 toxicities, and grade 5 (death) regardless of study phase or attribution.

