7.6 Routine Adverse Event Reporting

All Adverse Events **must** be reported in routine study data submissions to the Overall PI on the toxicity case report forms. **AEs reported through expedited processes (e.g., reported to the IRB, FDA, etc.) must** also be reported in routine study data submissions.

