13.1 Study Design/Endpoints

Primary endpoints:

- Determine the RP2D of these immunotherapy combinations for further testing
- Complete response rate using 2014 Lugano criteria

Secondary endpoints:

- Efficacy as measured by the objective, complete and partial response, stable disease and progressive disease rates by 2014 Lugano and LyRIC criteria, rate of MRD negativity at 6 and 12 months, 2-year progression free survival (by 2014 Lugano and LyRIC), overall survival and time to next treatment response duration
- Safety categorized by the rate of:
 - Grade 3 and higher toxicities, both regardless of attribution, and at least possibly attributed to the study treatment
 - Grade 2 or higher toxicity at least probably related to study treatment.
 - Adverse events leading to discontinuation due to toxicity.

Correlative or exploratory endpoints (when possible):

- Correlation between overall and complete response rates and MRD negativity and histologic grade (1-2 versus 3A) and FLIPI
- Calculation of the m7-FLIPI and correlation with overall and complete response rate and MRD negativity
- Comparisons of the tumor microenvironment composition and gene expression pre- and on-treatment
- Comparisons of the composition of the circulating immune environment, including the T cell repertoire, in the peripheral blood pre- and on-treatment
- Exploration of genetic markers of tumor response or resistance to therapy through whole exome sequencing
- Correlation between fecal microbiome and response or resistance to therapy

All exploratory or correlative endpoints will be analyzed descriptively.

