3.9 Safety Assessments and Toxicity Monitoring

The study teams at all participating institutions are responsible for protecting the safety, rights and well-being of study participants. Recording and reporting of adverse events that occur during the course of a study help ensure the continuing safety of study participants.

All participants receiving investigational agents and/or other protocol mandated therapy will be evaluated for safety. The safety parameters include all laboratory tests and hematological abnormalities, physical examination findings, and spontaneous reports of adverse events reported by participants. All toxicities encountered during the study will be evaluated according to the NCI criteria specified in the protocol. Life-threatening toxicities must be reported immediately to the DF/HCC Sponsor via the Coordinating Center.

Additional safety assessments and toxicity monitoring will be outlined in the protocol.

3.9.1 Guidelines for Reporting Serious Adverse Events

Guidelines for reporting Adverse Events (AEs) and Serious Adverse Events (SAEs) are detailed in protocol section 7.

Participating Institutions must report the SAEs to the DF/HCC Sponsor and the Coordinating Center following the DFCI IRB Adverse Event Reporting Policy.

The Coordinating Center will maintain documentation of all Participating Institution Adverse Event reports and be responsible for communicating to all participating investigators, any observations reportable under the DFCI IRB Reporting Requirements. Participating Institutions will review and submit to their IRB according to their institutional policies and procedures

3.9.2 Guidelines for Processing IND Safety Reports

The DF/HCC Sponsor will review all IND Safety Reports and ensure that all IND Safety Reports are distributed to the Participating Institutions. Participating Institutions will review/submit to their IRB according to their institutional policies and procedures.

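### Section 7.2 puts an undefined clinical-significance filter on laboratory values, while the grade 3 or higher toxicity endpoint is defined by CTCAE grade alone; the rate may be biased downward and vary by site.

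*Combined protocol and SAP*

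**What the plan says.** **The filter.** Section 7.2 (Adverse Event Reporting) says that events "detected through physical examination, laboratory test, or other means will be assessed and reported, when appropriate", and continues: "Abnormal laboratory values will not be reported unless deemed to be clinically significant". The section does not define clinical significance, does not say who judges it, and does not set grade 3 or 4 values apart. It is not confined to expedited notices: its introduction to the reporting requirements covers both entry of safety events on the case report form and onward reporting, and includes non-serious events.

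**The endpoint.** Section 1.3 lists "Rate of grade 3 or higher toxicity regardless of attribution" as a secondary safety objective. Section 13.1 repeats it as "Grade 3 and higher toxicities, both regardless of attribution, and at least possibly attributed to the study treatment". Neither adds a condition of clinical significance.

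**The other recording rules.**
- Section 5.1: "Toxicity will be continuously monitored and recorded using CTCAE 4 criteria".
- Section 7.6: all adverse events must "be reported in routine study data submissions to the Overall PI on the toxicity case report forms".
- Appendix C, Section 3.9: "The safety parameters include all laboratory tests and hematological abnormalities", and "All toxicities encountered during the study will be evaluated according to the NCI criteria specified in the protocol".

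**The concern.** The endpoint depends on grade; the reporting rule depends on judgement. A laboratory value can be CTCAE grade 3 or 4 without symptoms, and such a value counts toward the endpoint as defined. Under Section 7.2 the same value can be withheld because someone regards it as not clinically significant. The documents do not say which rule produces the analysis data.

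Two things are at stake. First, a filter of this kind can only remove events, so any error lowers the reported rate. Second, an undefined judgement made at several institutions can be applied differently, so part of a difference between cohorts could reflect reporting habit. This matters because the trial is meant to pick promising combinations empirically (Section 2.2) from cohorts of 15 (Section 13.2), and the grade 3 or higher rate is one of its main published safety descriptions.

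**Working it through.** **1. Is there a planned figure to reproduce?** Not for this endpoint. Section 13.2 gives no expected value, threshold, power or precision for the grade 3 or higher rate. The nearest figures concern DLTs with n = 15:
- P(X ≤ 3) = Σ C(15,x) pˣ(1−p)¹⁵⁻ˣ over x = 0 to 3. This gives 0.944 at p = 0.10 and 0.0905 at p = 0.40 (plan: 0.94 and 0.09).
- The widest exact (Clopper-Pearson) 90% interval has half-width 0.228, at 7 or 8 of 15 (plan: 23%).

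These figures rest on DLT counts, so the point raised here does not change them.

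**2. The rules side by side.**

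| Place | Rule for a grade 3-4 laboratory value |
|---|---|
| 1.3, 13.1 | Counts toward the rate if it is a toxicity of that grade, whatever the attribution |
| 5.1 | Recorded by CTCAE grade, no significance condition |
| 7.6 | On the toxicity form if it is an adverse event |
| 7.2 | Not reported unless deemed clinically significant |

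Section 7.6 does not settle the conflict. If a site concludes under 7.2 that a value is not reportable, it may never be treated as an adverse event that 7.6 would send to the form. Table 5 is only a partial backstop: expected grade 2-3 events need no report at any attribution, nor do unexpected grade 2-3 events judged unrelated or unlikely to be related.

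**3. Which values are exposed?** Section 10.2 schedules blood counts and chemistries at each planned cycle 1 visit and on days 1 and 15 of cycles 2-6, with CK, lipase and triglycerides on day 1 of each cycle. Amylase is not named in that list, so it is exposed only where it is measured. The protocol itself foresees symptom-free events: the note to Table 4 deals with asymptomatic grade 4 lipase, amylase and CK elevations. The DLT definition in Section 5.1 exempts grade 3 hematologic abnormalities and grade 3 or higher amylase or lipase without pancreatitis. These exempted events still fall within the secondary endpoint but carry no DLT consequence, so they are the easiest to judge insignificant.

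**4. Size, by assumption only.** Let p be the true proportion of patients with any grade 3 or higher toxicity. Let s be the share of those patients whose only such event is a laboratory value left unreported. Then the reported rate is p(1−s), and the expected number missed of 15 is 15ps. Neither p nor s is in the documents.

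| p | s = 0 | s = 0.10 | s = 0.25 | s = 0.50 |
|---|---|---|---|---|
| 0.20 | 0.20 (0) | 0.18 (0.3) | 0.15 (0.75) | 0.10 (1.5) |
| 0.40 | 0.40 (0) | 0.36 (0.6) | 0.30 (1.5) | 0.20 (3.0) |
| 0.60 | 0.60 (0) | 0.54 (0.9) | 0.45 (2.25) | 0.30 (4.5) |

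Entries are the reported rate, with expected patients missed in parentheses. For scale, the exact 90% interval is 0.191 to 0.640 for 6 of 15 and 0.057 to 0.440 for 3 of 15. Sampling error is therefore large in any case, but the interval makes no allowance for missing events.

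**The case against.** The strongest reply is that the plan already requires these events and that the exposed set is small. Much of it stands.

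- **Recording is required elsewhere.** Sections 5.1 and 7.6 call for toxicity to be recorded and for all adverse events to go on the form, and much of 7.2 concerns notification. So a reader who infers that the rate *is* undercounted goes further than the documents allow. They show conflicting rules, not a known omission. Nor are the results lost: the tests are still done on schedule.
- **Most treatment-related values force action.** Tables 3 and 4 attach a hold or discontinuation to treatment-related grade 3 or higher toxicities, including liver tests and hematologic values, and Section 6 requires dose modifications to be documented on the case report form. Section 6.5 also restricts starting a new treatment, without reference to attribution. A value that interrupts treatment is hard to call insignificant. What remains is mainly values not attributed to treatment, or seen between treatments; Tables 3 and 4 cover treatment-related toxicity, whereas the endpoint ignores attribution.
- **DLTs.** A reader might infer that DLT counts are affected too. The documents do not support this: DLTs have their own grade-based definition, and a grade 4 hematologic event that fails to recover is unlikely to be dismissed.
- **Appendix C.** It is tempting to call 7.2 a breach of Appendix C. The appendix does list all laboratory tests as safety parameters, but it sends the reader back to Section 7 for reporting guidelines, so it is weak evidence of contradiction.
- **Consequences.** The tolerability rules in Section 13.2 use DLT or excessive-toxicity counts (3 or fewer of 15 in part A, 2 or fewer in part B). No go/no-go rule uses the grade 3 or higher rate.

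The reply does not remove the core conflict. Section 7.2 is an explicit rule with no grade exception, it reaches entry on the case report form, and nothing says that 5.1 or 7.6 overrides it.

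**Conclusion.** The point holds as a risk to a secondary endpoint. Followed as written, Section 7.2 may leave out asymptomatic or unattributed grade 3 or higher laboratory events, chiefly lipase, amylase, CK, triglycerides and some hematologic values. Any bias is downward and may differ by site.

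The size is unknown. It is zero if sites record by grade under Section 5.1, and each patient missed in a cohort of 15 costs 6.7 percentage points. The illustrative rates above rest wholly on assumed p and s and are not estimates. The conclusion assumes that no other instruction, such as form-completion guidance outside these documents, already requires grade-based entry. The sentence in 7.2 does not say that the investigator decides; the absence of any named decision-maker is part of the problem. The DLT-based decision rules are not shown to be affected.

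**What to change.** **Section 7.2.** Limit the clinical-significance condition to expedited reporting, or to grade 1-2 values. Add that every CTCAE grade 3 or higher laboratory value that is a worsening from the patient's baseline grade is recorded on the toxicity form, whatever its judged significance. Limiting the condition to expedited reporting is the cleaner choice, because Section 13.1 also has a rate of grade 2 or higher toxicity at least probably related to treatment, which a filter kept on grade 2 could still touch.

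**Section 13.1.** State that the grade 3 or higher rates include these laboratory events, and define the baseline value.

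The baseline condition is needed. Section 3.1.8 admits patients with lower neutrophil and platelet counts when marrow involvement is the cause, and the note to Table 3 sets lymphoma-related cytopenias apart. Grading every result without regard to baseline would count pre-existing cytopenias as toxicity and replace a possible downward bias with an upward one.

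**Cost.** A short change in each section, slightly more data entry, and somewhat higher reported rates. The tests are already scheduled, and no treatment or DLT rule changes.

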7.2.1 DF/HCC Adverse Event Reporting Guidelines

Investigative sites within DF/HCC will report AEs directly to the DFCI Office for Human Research Studies (OHRS) per the DFCI IRB reporting policy.

Other investigative sites will report AEs to their respective IRB according to the local IRB's policies and procedures in reporting adverse events. A copy of the submitted institutional AE form should be forwarded to the Overall PI within the timeframes detailed in the table below.

		Table 5. DF/HCC Reportable Adverse Events(AEs)										
Attribution	Gr. 2 & 3 AE Expected	Gr. 2 & 3 AE Unexpected	Gr. 4 AE Expected	Gr. 4 AE Unexpected	Gr. 5 AE Expected or Unexpected							
Unrelated Unlikely	Not required	Not required	10 working days [#]	10 working days	24 hours*							
Possible Probable Definite	Not required	10 working days	10 working days [#]	10 working days	24 hours*							

The Overall PI will submit AE reports from outside institutions to the DFCI OHRS according to DFCI IRB policies and procedures in reporting adverse events.

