- Grade 3 hypertension controlled by medical therapy;
- O Grade 3 diarrhea that improves to Grade ≤2 within 72 hrs after medical management has been initiated;
- Grade 3 skin toxicity that resolves to Grade ≤1 in less than 7 days after medical management (eg, immunosuppressant treatment) has been initiated;
- Any Grade \geq 3 amylase or lipase abnormality that is not associated with symptoms or clinical manifestations of pancreatitis;
- Grade 3 endocrinopathies controlled with medical therapy;
- Tumor flare phenomenon defined as local pain, irritation, or rash localized at sites of known or suspected tumor.
- Non-hematologic Grade \geq 3 laboratory abnormality if medical intervention is required to treat the patient or the abnormality leads to hospitalization.
 - Single laboratory values out of normal range that are unlikely related to trial treatment according to the Investigator, do not have any clinical correlate, and resolve to Grade ≤1 within 7 days with adequate medical management are not to be considered DLTs;
- ALT or AST >3 x upper limit of normal (ULN) (if normal at baseline) or >3 x ULN and doubling the baseline (if > ULN at baseline) associated with bilirubin >2 x ULN

For part B (untreated disease cohorts), enrollment will open following the completion of the corresponding dose expansion cohort in part A (cohorts A1b and A2b), assuming that the corresponding cohort in part A meets its efficacy and safety criteria for success (\geq 3 complete responses and \leq 3 DLTs).

All cohorts in part B will have an early stopping rule if >2 patients at any point meet the criterion for a DLT.

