7.4 Expedited Reporting to Pfizer

Within 24 hours of first awareness of the event (immediately if the event is fatal or lifethreatening), the study team will report to Pfizer by facsimile any Serious Adverse Event ("SAE," as defined below) for which reporting is required under this provision (as described below). Such SAEs are to be reported for study subjects or individuals otherwise exposed to the Pfizer Product as described below. The study teams should report SAEs as soon as they are determined to meet the definition, even if complete information is not yet available.

Study teams will report SAEs using Form FDA 3500A (MedWatch). The *Reportable Event Fax Cover Sheet* provided by Pfizer must also be included with each SAE submitted.

7.4.1 SAE Definition for Reporting to Pfizer

An SAE is any adverse event, without regard to causality, that is life-threatening (ie, causes an immediate risk of death) or that results in any of the following outcomes: death; in-patient hospitalization or prolongation of existing hospitalization; persistent or significant disability or incapacity (i.e., substantial disruption of the ability to conduct normal life functions); or a congenital anomaly or birth defect. Any other medical event that, in the medical judgment of the Principal Investigator, may jeopardize the subject or may require medical or surgical intervention to prevent one of the outcomes listed above is also considered an SAE. A planned medical or surgical procedure is not, in itself, an SAE.

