12.2 Data Safety Monitoring

The DF/HCC Data and Safety Monitoring Committee (DSMC) will review and monitor toxicity and accrual data from this study. The committee is composed of medical oncologists, research nurses, pharmacists and biostatisticians with direct experience in cancer clinical research. Information that raises any questions about participant safety will be addressed with the Overall PI and study team.

The DSMC will review each protocol up to four times a year with the frequency determined by the outcome of previous reviews. Information to be provided to the committee may include: up-to-date participant accrual; current dose level information; DLT information; all grade 2 or higher unexpected adverse events that have been reported; summary of all deaths occurring within 30 days of intervention for Phase I or II protocols; for gene therapy protocols, summary of all deaths while being treated and during active follow-up; any response information; audit results, and a summary provided by the study team. Other information (e.g. scans, laboratory values) will be provided upon request.

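### No deadline assures that a DLT at an outside site reaches the Overall PI before further Part B patients start, although Part B must close once more than two patients have a DLT

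*Combined protocol and SAP*

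**What the plan says.** **The stopping rule.** Section 5.1: "All cohorts in part B will have an early stopping rule if >2 patients at any point meet the criterion for a DLT". Section 13.2 judges a Part B combination safe if 2 or fewer of 15 patients have excessive toxicity, with a null rate of 35%, an alternative of 10%, 82% power and 6% one-sided error.

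**What counts as a DLT.** Section 5.1 counts any toxicity of grade 3 or more that is not incontrovertibly due to progression, subject to a list of exceptions.

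**How events reach the Overall PI.**
- Section 7.2.1, for outside sites: "A copy of the submitted institutional AE form should be forwarded to the Overall PI within the timeframes detailed in the table below". In Table 5 the column headed "Gr. 2 & 3 AE Expected" reads not required in both attribution rows. Grade 4 events, expected or not, have 10 working days. Grade 5 events have 24 hours.
- Section 7.2, on the general duty of sites: "report to the Overall PI any adverse event (AE) that occurs after the initial dose of study treatment, during treatment, or within 30 days". The 30 days count from the final dose and bound which events are covered; no time limit for sending the report is attached.
- Section 7.2, on the DF/HCC requirement for multi-center trials: "This applies to any medical event equivalent to an unexpected grade 2 or 3 with a possible, probable or definite attribution", together with unexpected grade 4 and grade 5 events. Expected grade 3 is not named.
- Section 7.6, on every adverse event without exception: "be reported in routine study data submissions to the Overall PI on the toxicity case report forms". Again no time limit is given.
- Section 7.4: within 24 hours, "the study team will report to Pfizer by facsimile any Serious Adverse Event". This route goes to the drug supplier.
- Section 7.2 and Appendix C section 3.9: immediate notice to the Overall PI or Sponsor covers unanticipated problems and life-threatening events.

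**Oversight.** Section 12.2: "The DSMC will review each protocol up to four times a year".

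**The concern.** The Part B rule is a running count across several institutions, so it can act only on DLTs that the center knows about. A grade 3 event can be both a DLT and expected. Pneumonitis and infusion reactions, for example, are listed in section 7.1.1, and the exceptions in section 5.1 do not name them. For such an event the one table with timeframes asks for no timed forwarding. The two provisions that do cover it (7.2 and 7.6) have no clock. For grade 4, the stated limit is two working weeks.

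The dose-escalation stage has a safety pause after each group of three patients. Section 5.1 describes none for Part B. If the third DLT is still in transit, the cohort can go on enrolling past the point at which its own rule closes it. What is at stake is avoidable exposure of previously untreated patients.

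**Working it through.** **1. Routes for an expected, non-life-threatening grade 3 DLT at an outside site**

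| Route | Covers it? | Time limit to the Overall PI |
|---|---|---|
| Table 5 (7.2.1) | Marked not required | None |
| Any-AE duty (7.2) | Yes | None stated |
| Routine case report forms (7.6) | Yes | None stated |
| Immediate notice (7.2, Appendix C 3.9) | Only if an unanticipated problem or life-threatening | Immediate |
| SAE to the drug supplier (7.4) | Only if serious | 24 hours, but not to the Overall PI |
| SAE to Sponsor and Coordinating Center (Appendix C 2.3, 3.9.1) | Only if serious | By DF/HCC and IRB policy; no DLT limit given |
| DSMC (12.2) | DLT data may be supplied | At most four reviews a year |

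No row gives a fixed time for a DLT as such.

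**2. Reproducing the plan's figures**

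Inputs from section 13.2: n = 15, safe if X ≤ 2, rates 10% and 35%.

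P(X ≤ 2) = Σ (k = 0 to 2) C(15,k) p^k (1−p)^(15−k)

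- p = 0.10: 0.2059 + 0.3432 + 0.2669 = 0.816 (plan: 0.82).
- p = 0.35: 0.0016 + 0.0126 + 0.0476 = 0.062 (plan: 0.06).

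All seven cells of the Part B toxicity table reproduce.

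**3. Patients treated before closure**

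Let N be the position of the patient with the third DLT:

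P(N = n) = C(n−1, 2) p³ (1−p)^(n−3), for n = 3 to 15.

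Let L be the number of further patients who start before that DLT is known to the center. L is an assumption, because the documents give no reporting lag and no Part B accrual rate. Then

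E(treated) = Σ P(N = n) · min(15, n + L) + 15 · P(no third DLT in 15).

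At p = 0.35, P(no third DLT in 15) = 0.062, so the rule closes the cohort with probability 0.938.

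| L | Mean treated | Excess over L = 0 |
|---|---|---|
| 0 | 8.35 | – |
| 1 | 9.27 | 0.9 |
| 3 | 11.00 | 2.7 |
| 5 | 12.54 | 4.2 |
| 7 | 13.78 | 5.4 |
| 12 or more | 15.00 | 6.65 |

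Without the cap the third DLT would come on average at patient 3/0.35 = 8.6. Adding L to that figure overstates the excess, because no cohort goes beyond 15.

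At lower true rates the excess is smaller. For L = 5 it is 14.20 − 12.00 = 2.2 at 20%, and 14.85 − 14.29 = 0.6 at 10%.

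**4. Effect on the verdict**

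A cohort fails if a third DLT occurs among its 15 patients, whenever that DLT becomes known. Delay alone therefore leaves the 82% and 6% as they are.

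**The case against.** The strongest reply is that the plan has more channels than Table 5. Section 7.2 places a duty on investigators to report every adverse event to the Overall PI, and 7.6 repeats it for routine data. Many grade 3 events will be serious: Table 2 calls for hospitalization in grade 3 to 4 pneumonitis, and hospitalization makes an event an SAE. Participating institutions send SAEs to the Sponsor and Coordinating Center. Section 5.1 has toxicity monitored continuously, Appendix C requires regular teleconferences, outside patients are registered centrally, and closures take effect at once. Some detail is also out of sight: the footnotes to Table 5, a reporting table announced in 7.2, and the DF/HCC policies on data submission and SAE reporting.

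Much of this stands, and it rules out several stronger readings:

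- **That expected grade 3 events need not reach the Overall PI.** Sections 7.2 and 7.6 require it. What is missing is a time.
- **That most immune-related DLTs are expected grade 3 events.** The documents give no such share. Section 5.1 takes several grade 3 immune-type events out of the DLT definition (controlled endocrinopathy, diarrhea that improves within 72 hours, skin toxicity that resolves in under 7 days). Section 7.1.2 can also make a listed event unexpected by its severity.
- **That the rule cannot act in time.** It may well do so through the other channels. The plan does not assure it.
- **That the Part A expansion is affected in the same way.** Section 13.2 judges it on all 15 patients, and section 5.1 gives it no running closure rule that a delay could defeat.

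What the reply does not supply is a stated time for a DLT to travel from site to center. The SAE routes miss DLTs that are not serious, and the fastest of them goes to the drug supplier. Continuous monitoring and teleconferences set no deadline. The registration steps in 4.4 and Appendix C 3.7 do not mention a DLT count.

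**Conclusion.** The point holds in a limited form. The timeframes that the plan does state do not support a rule that must act at any point, and section 7.2 and Table 5 need to be reconciled. Timely closure of a Part B cohort is possible but not assured.

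At the 35% rate, the added exposure is about 1 to 5 patients per cohort if 1 to 7 more start before the third DLT is known. A reader might infer 7 or more extra patients from lag times accrual, but the 15-patient cap does not allow that: even if the cohort always fills, the mean excess is 15 − 8.35 = 6.65.

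These figures rest on an assumed lag. They also treat each DLT as occurring at once in the patient concerned and the third as reaching the center only by the slow route. DLTs that appear late would add some exposure under any reporting rule. The safety verdict on 15 patients, with its 82% and 6%, is unaffected. The change is worth making because it is cheap and protects patients, not because the analysis is invalid.

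**What to change.** 1. Reconcile section 7.2 with Table 5, so that it is clear which events outside sites send to the Overall PI and by when.
2. Add one line to 7.2 (or 5.1) and one row to Table 5: any event that meets or may meet the section 5.1 DLT definition, whatever its grade or expectedness, is notified to the Overall PI and Coordinating Center within a short fixed limit set by the sponsor.
3. Add one step to central registration (4.4 and Appendix C 3.7): the Coordinating Center checks the cohort's current DLT count before it confirms each Part B registration.

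The cost is a small amount of extra reporting for sites and one check in a process that already exists. Sample size, thresholds and operating characteristics stay as they are.
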